clopidogrel between 3 and 24 hours prior to the index procedure or prasugrel or ticagrelor between 1-24 hours prior to the index procedure OR b) an intravenous GP IIb/IIIa inhibitor or cangrelor (see below) prior to and/or during PCI but prior to first balloon inflation, per institution standard of care.. If an intravenous GP IIb/IIIa inhibitor is given, a P2Y12 receptor inhibitor must be given within 1 hour following the index procedure. If intravenous cangrelor is used, the timing of the first administration of the P2Y12 receptor inhibitor should be as follows: clopidogrel or prasugrel are administered at the time of discontinuation of the cangrelor infusion; ticagrelor may be administered before, during, or immediately upon discontinuation of the cangrelor infusion. Ticagrelor is the preferred P2Y12 receptor inhibitor in cangrelor-treated patients. Cangrelor should be maintained 2-4 hours post procedure according to product labeling. Note: If the subject receives less than the required amount of the loading dose for a P2Y12 receptor inhibitor, the investigator is to give the remaining amount of the same agent in the next 24 hours and within the protocol required timeframe.

- The protocol required loading dose may be omitted in a) stable CAD or ACS patients maintained on chronic P2Y12 receptor inhibitor for  $\geq$  7 days, and b) patients who received a P2Y12 receptor inhibitor loading dose 1-7 days prior to the procedure and who have been maintained on a daily dose since. However, it is strongly recommended that stable patients on chronic clopidogrel are reloaded with a P2Y12 receptor inhibitor. For ACS patients on chronic clopidogrel, they must be reloaded with a P2Y12 receptor inhibitor if they did not already receive a loading dose of clopidogrel, prasugrel, or ticagrelor in the 24 hours prior to the procedure
- Ticlopidine may be used as a substitute at a dose in accordance with standard hospital practice only if the subject develops hypersensitivity or intolerance to clopidogrel, prasugrel, or ticagrelor during the trial.
- Refer to respective prescribing information for P2Y12 receptor inhibitor for further details regarding loading practice.

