- Cangrelor may be used pre-PCI at operator discretion as per local practice in any patient (but should be used similarly in patients randomized to ABSORB and XIENCE): a pre-PCI loading dose of 30  $\mu$ g/kg IV followed by an IV infusion of 4  $\mu$ g/kg for at least 2 hours and for a maximum of 4 hours may be used, in conjunction with an oral P2Y12 inhibitor. If ticagrelor is selected, the ticagrelor loading dose may be given before, during or immediately upon discontinuation of the cangrelor infusion. If clopidogrel or prasugrel

	
are selected, a clopidogrel or prasugrel loading dose should be given immediately upon discontinuation of the cangrelor infusion, even if a loading dose was given earlier.
 
Antiplatelet Medication Post-Procedure Daily Dose:
 

• All subjects must be maintained at a minimum of 75 mg of clopidogrel daily or 5 or 10 mg of prasugrel daily (10 mg preferred in most patients*) or 90 mg twice daily of ticagrelor for a minimum of 12 months following the procedure.

• All subjects must receive <math>\geq 75</math> to <math>\leq 100</math> mg of aspirin daily through 5 years follow-up during the study and should continue to take aspirin indefinitely.

 
*For prasugrel subjects <math>< 60</math> kg in weight or <math>\geq 75</math> years of age a maintenance dose of 5 mg per day for 12 months is recommended. Patients with prior stroke or TIA should receive clopidogrel or ticagrelor, and cannot be administered prasugrel.
 
Refer to respective prescribing information for P2Y12 receptor inhibitor for further details regarding maintenance dose.
 
For subjects having staged procedures, the protocol-required pre-procedure and post-procedure antiplatelet regimens must be repeated for the staged procedure in the same manner as done for the original index procedure.

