### **7.2.2 Dual Anti-Platelet Medications**

Subjects selected for treatment with Absorb BVS or XIENCE must receive a loading dose of  $\geq$  300 mg of aspirin within 24 hours, regardless of whether the patient was previously taking aspirin. For patients undergoing staged procedure who have not been discharged and have been prescribed daily aspirin while in hospital, no aspirin reloading is required.

For patients with stable coronary symptoms, silent ischemia, or acute coronary syndromes in whom all measured troponin and CK-MB values were within normal limits, pre-loading with clopidogrel between 3 and 24 hours prior to the index procedure or prasugrel or ticagrelor between 1-24 hours prior to the index procedure is strongly recommended. If the above loading time periods are not possible, the P2Y12 inhibitor must be administered in all patients no later than 1 hour after the procedure. If the subject receives less than the required amount of the loading dose for a P2Y12 receptor inhibitor, the investigator is to give the remaining amount of the same agent in the next 24 hours and within the protocol required timeframe.

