**Confidential and Proprietary**

**Do not distribute or reproduce without the prior written permission of Abbott Vascular Inc.**

**ABSORB III Randomized Control Trial Version 17.0 August 16, 2018.**

Note: The biomarker measurements in patients with stable coronary symptoms and silent ischemia may be pending at the time of the procedure, or may be drawn from the arterial sheath prior to first balloon inflation; such patients may still be randomized, and a P2Y12 receptor inhibitor must be administered no later than 1 hour after the procedure.

For patients with acute coronary syndromes in whom any troponin or CK-MB value at any time prior to the index hospitalization was elevated, one of two treatment options must be used a) a loading dose of clopidogrel between 3 and 24 hours prior to the procedure or prasugrel or ticagrelor between 1-24 hours prior to the index procedure must be given, OR b) an intravenous GP IIb/IIIa inhibitor or cangrelor (see below) must be administered prior to and/or during PCI but prior to first balloon inflation, per institution standard of care. If an intravenous GP IIb/IIIa inhibitor is given, a P2Y12 receptor inhibitor must be given within 1 hour following the index procedure. If intravenous cangrelor is used, the timing of the first administration of the P2Y12 receptor inhibitor should be as follows: clopidogrel or prasugrel are administered at the time of discontinuation of the cangrelor infusion; ticagrelor may be administered before, during, or immediately upon discontinuation of the cangrelor infusion. Ticagrelor is the preferred P2Y12 receptor inhibitor in cangrelor-treated patients. Cangrelor should be maintained 2-4 hours post procedure according to label.

Note: If the subject receives less than the required amount of the loading dose for a P2Y12 receptor inhibitor, the investigator is to give the remaining amount of the same agent in the next 24 hours and within the protocol required timeframe.

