The protocol required loading dose may be omitted in a) stable CAD or ACS patients maintained on chronic P2Y12 receptor inhibitor for  $\geq$  7 days, and b) patients who received a P2Y12 receptor inhibitor loading dose 1-7 days prior to the procedure and who have been maintained on a daily dose since. However, it is strongly recommended that stable patients on chronic clopidogrel are reloaded with a P2Y12 receptor inhibitor. For ACS patients on chronic clopidogrel, they must be reloaded with a P2Y12 receptor inhibitor if they did not already receive a loading dose of clopidogrel, prasugrel, or ticagrelor in the 24 hours prior to the procedure.

Ticlopidine may be used as a substitute at a dose in accordance with standard hospital practice only if the subject develops hypersensitivity or intolerance to clopidogrel, prasugrel, or ticagrelor during the trial.

Refer to respective prescribing information for P2Y12 receptor inhibitor for further details regarding loading practice.

Cangrelor may be used pre-PCI at operator discretion as per local practice in any patient (but should be used similarly in patients randomized to ABSORB and XIENCE): a pre-PCI loading dose of 30  $\mu$ g/kg IV followed by an IV infusion of 4  $\mu$ g/kg for at least 2 hours and for a maximum of 4 hours may be used, in conjunction with an oral P2Y12 inhibitor. If ticagrelor is selected, the ticagrelor loading dose may be given before, during or immediately upon discontinuation of the cangrelor infusion. If clopidogrel or prasugrel are selected, a clopidogrel or prasugrel loading dose should be given immediately upon discontinuation of the cangrelor infusion, even if a loading dose was given earlier.

For subjects having staged procedures, the pre-procedure administration regimen of aspirin and P2Y12 receptor inhibitor (dosage requirements and timing) must be repeated prior to the staged

procedure in the same manner as done for the original index procedure. If the subject has not been discharged between the index and staged procedures, and has received daily aspirin while in hospital, no aspirin reloading is required (see above).

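### ABSORB IV prints the cangrelor infusion without a time unit, anchors its duration in two different ways, and does not say whether the 1-hour oral-agent limit applies when cangrelor is used

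*Combined protocol and SAP*

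**What the plan says.** The relevant text is in the ABSORB IV part: the Antiplatelet Therapy row of the Protocol Summary and section 7.2.2, which largely repeat each other.

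- **Any-patient paragraph.** Section 7.2.2 states that "Cangrelor may be used pre-PCI at operator discretion as per local practice in any patient". It gives a bolus of 30 µg/kg and then an infusion of 4 µg/kg "for at least 2 hours and for a maximum of 4 hours may be used". The Protocol Summary has the same figure and the same gap: 4 µ"g/kg for at least 2 hours and for a maximum of 4 hours may be used, in conjunction with an oral P2Y12 inhibitor".
- **Biomarker-positive ACS paragraph.** This one allows cangrelor as an alternative to pre-loading and points forward to the any-patient text. Section 7.2.2 says "Cangrelor should be maintained 2-4 hours post procedure according to label"; the Protocol Summary says "Cangrelor should be maintained 2-4 hours post procedure according to product labeling".
- **Oral agent with cangrelor.** For clopidogrel or prasugrel, "a clopidogrel or prasugrel loading dose should be given immediately upon discontinuation of the cangrelor infusion", even where the patient was already loaded. Ticagrelor may be given before, during or at the end of the infusion.
- **Oral agent in general.** For stable, silent-ischemia or biomarker-negative ACS patients who could not be pre-loaded in the recommended window, the P2Y12 inhibitor "must be administered in all patients no later than 1 hour after the procedure". A note applies the same limit to stable and silent-ischemia patients whose biomarkers are pending. Neither place mentions cangrelor.
- **Labeling.** A footnote in the Protocol Summary refers loading and maintenance dosages of P2Y12 inhibitors to prescribing information. The post-procedure duration sentence also cites the label.

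**The concern.** An amount per kilogram spread over 2 to 4 hours is not an infusion rate until a unit of time is attached, and the protocol attaches none. The duration has two anchors: one sentence bounds an infusion that starts before PCI, the other counts from the end of the procedure. The 1-hour limit on the oral agent carries no exception for patients whose clopidogrel or prasugrel is tied to the end of the infusion.

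These are operative instructions for an intravenous antiplatelet drug given around PCI, so incomplete or inconsistent text bears on patient safety. It also bears on conduct. Deviations must be reported (ABSORB III section 12.4, which ABSORB IV section 11 adopts), and a monitor could not say which sentence a given infusion breached. For the analysis, target-vessel MI is part of the 30-day primary endpoint (ABSORB IV section 5.1), and section 10.4.4 plans to relate thrombosis and bleeding events to antiplatelet therapy. The text asks for similar use of cangrelor in both arms, but the operator is not blinded (section 4.4.2). No sample size, power or alpha depends on this point.

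**Working it through.** The plan has no figure of its own to reproduce. The check is a comparison of the passages with simple arithmetic.

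**1. Missing unit.** Inputs: 4 µg/kg and 2 to 4 hours (both documents' places above). Body weight is not given; assume 80 kg, so 4 × 80 = 320 µg.

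- Read per minute: 320 × 120 = 38,400 µg (38.4 mg) to 320 × 240 = 76,800 µg (76.8 mg).
- Read per hour: 320 × 2 = 640 µg (0.64 mg) to 320 × 4 = 1,280 µg (1.28 mg).
- Read as a single total: 0.32 mg.

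Per-minute and per-hour readings differ by a factor of 60 at any weight. These are possible readings of ambiguous text; nothing here says which is right. Loss of the unit in text extraction is unlikely, because the gap is identical in two separate sections, but it is worth a glance at the PDF.

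**2. Duration.** Let p be the hours from infusion start to the end of the procedure. The documents do not give p; take 0.25 to 2.5.

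- Any-patient rule: total infusion 2 to 4 h, so time after the procedure is max(0, 2 − p) to 4 − p.
- Biomarker-positive ACS rule: 2 to 4 h after the procedure, so total infusion is p + 2 to p + 4.

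| p (h) | Post-procedure hours, any-patient rule | Post-procedure hours meeting both rules | Total hours, ACS rule |
|---|---|---|---|
| 0.25 | 1.75–3.75 | 2–3.75 | 2.25–4.25 |
| 0.5 | 1.5–3.5 | 2–3.5 | 2.5–4.5 |
| 1 | 1–3 | 2–3 | 3–5 |
| 1.5 | 0.5–2.5 | 2–2.5 | 3.5–5.5 |
| 2 | 0–2 | 2 only | 4–6 |
| 2.5 | 0–1.5 | none | 4.5–6.5 |

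Both rules can be met when 4 − p ≥ 2, that is p ≤ 2. For every p > 0 the upper end of the ACS rule (p + 4) is above the 4-hour maximum, and the shortest course under the any-patient rule ends less than 2 hours after the procedure.

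**3. Oral agent.** Take a stable or biomarker-negative patient, not pre-loaded, given cangrelor under the any-patient paragraph and then clopidogrel or prasugrel at discontinuation. With total infusion T between 2 and 4 h, discontinuation falls T − p hours after the procedure. Meeting the 1-hour limit needs T ≤ p + 1. Since T is at least 2, that requires p ≥ 1 and an infusion no longer than p + 1 hours. At p = 0.5 the earliest stop is 2 − 0.5 = 1.5 h after the procedure, outside the limit. At p = 1 only the minimum 2-hour infusion meets it.

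**The case against.** Several mitigating facts stand. Cangrelor is optional, and the number of users is not stated. The text points to labeling, which lowers the practical risk. But those pointers are general, the protocol still prints its own incomplete figure, and the label is cited for the very duration that differs from the other paragraph. Referring to it does not say which protocol sentence governs.

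Four stronger readings are tempting and are not supported.

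- *The cangrelor instructions contradict each other on the timing of the oral agent.* They do not. Both paragraphs place clopidogrel or prasugrel at discontinuation and allow ticagrelor before, during or at the end of the infusion. The conflict is with the general 1-hour limit.
- *A site cannot comply with everything at once.* The duration rules overlap for p up to 2 hours. Ticagrelor, which the text prefers for cangrelor-treated patients, can be given in time. The any-patient paragraph also foresees an earlier load, so a clopidogrel or prasugrel load inside the hour, with another at discontinuation, is not textually excluded.
- *The oral agent is 1 to 3 hours late.* Subtracting 1 hour from the 2-to-4-hour post-procedure rule joins a duration written for biomarker-positive ACS to a limit written for stable or biomarker-negative patients. The biomarker-positive paragraph sets its own cangrelor timing; its 1-hour limit attaches to GP IIb/IIIa inhibitors.
- *Stent thrombosis is part of the primary endpoint.* Target lesion failure comprises cardiac death, target-vessel MI and ischemia-driven target lesion revascularization. Thrombosis is a separate secondary endpoint (section 5.3).

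**Conclusion.** The point holds in three parts of unequal weight. The missing time unit is certain, occurs twice, leaves a 60-fold spread between two readings, and by itself justifies a correction. The duration rules are partly inconsistent: they are compatible for p up to 2 hours and incompatible beyond it, and the upper end of the post-procedure rule exceeds the 4-hour maximum for any p above zero. This matters for biomarker-positive ACS patients, who fall under both paragraphs. The oral-agent gap is narrower: it concerns clopidogrel or prasugrel in stable or biomarker-negative patients who were not pre-loaded or whose biomarkers are pending.

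The results assume that the 2-to-4-hour bound in the any-patient paragraph is total infusion time. The values of p and the 80 kg weight are illustrative. No effect on the endpoint comparison can be sized, because cangrelor use is not stated. This is a drafting defect with safety relevance; it does not affect any statistical figure in the plan.

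**What to change.** Reconcile the Antiplatelet Therapy row of the ABSORB IV Protocol Summary with section 7.2.2 in a single edit, so that both places:

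1. give the infusion with its full unit, including time;
2. state one duration rule with an explicit start point, and the patients to whom it applies;
3. say whether the 1-hour post-procedure limit applies to cangrelor-treated subjects who receive clopidogrel or prasugrel.

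The sponsor's clinical team must choose the values and the rule; none is proposed here. The cost is a clarification letter or amendment wording. Sample size and the planned analyses are unchanged.

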### **7.2.3 Anticoagulation Medications**

Subjects must receive appropriate anticoagulation and other therapy according to standard hospital practice. Either unfractionated heparin or bivalirudin may be used for procedural anticoagulation, as per the discretion of the investigator. Subjects having been treated with low molecular weight heparin (LMWH) prior to the procedure should receive their last dose more than 8 hours prior to the index procedure, and then be anticoagulated during the procedure with either unfractionated heparin or bivalirudin. LMWH and fondaparinux are not permitted as procedural anticoagulants in this protocol.

Use of glycoprotein IIb/IIIa inhibitors will be at the discretion of the investigator for stable patients. Patients with biomarker positive acute coronary syndromes in whom procedural anticoagulation is achieved with unfractionated heparin should receive a procedural glycoprotein IIb/IIIa inhibitor dosed per standard of care. Glycoprotein IIb/IIIa inhibitors should not routinely be used in bivalirudin anticoagulated patients unless 1) the patient had an acute coronary syndrome and did not receive recommended pre-loading with a P2Y12 receptor inhibitor (and in whom cangrelor is not used during the PCI); and/or 2) refractory ischemic and/or thrombotic complications develop during the procedure.

### **7.2.4 Statin Therapy**

In the absence of absolute contraindications to statin use (e.g. severe allergy with prior use), it is strongly recommended to preload with statins 12 hours prior to the procedure regardless of LDL level and history of prior or current statin use. Recommended statin loading dose regimens include atorvastatin 80 mg or rosuvastatin 40 mg.

## **7.3 Index Procedure**

### **7.3.1 Baseline (Pre-Procedure) Angiography**

Baseline angiography of the target vessel(s) will be completed as per the Angiographic Core Laboratory Protocol.

### **7.3.2 Imaging Guidance Document**

The Imaging Guidance Document will provide specific details and instructions from the angiographic core laboratory regarding vessel sizing. This document will be separate from the protocol.

### **7.3.3 Treatment Rules of the Target Lesion(s)**

Please see **Protocol Summary**, Treatment Strategy, for details of the treatment rules of target lesion(s).

### **7.3.4 Treatment Rules of Unplanned Non-Target Lesion(s)**

In situations where treatment of a planned target lesion revealed additional lesion(s), the additional lesion(s) may be treated. These lesions are considered unplanned lesions. If the lesion meets enrollment criteria both before and after pre-dilatation, the lesion must be treated with the assigned device and will be considered as an unplanned target lesion. If the lesion does not meet the enrollment criteria (either before or after pre-dilatation), the lesion must be treated with XIENCE and will be considered as an unplanned non-target lesion.

### **7.3.5 Bailout Stenting or Alternative Procedures**

Bailout procedures may be performed if the subject experiences:

- Dissection requiring intervention
- Occlusive complication as evidenced by a decrease in target vessel flow
- Chest pain or ischemic changes measured by ECG that do not respond to repeat balloon inflations, medical therapy or lytic agents
- Unplanned additional device is required to cover the target lesion

During randomization, if a bailout device is required for a target lesion (e.g., for edge dissection), the same device as the implanted device must be used. Overlap of the bailout stent/scaffold with the implanted stent/scaffold should be 1-2 mm. Gaps should be avoided.

- o Use Absorb BVS if target lesion is treated with Absorb BVS.
- o Use XIENCE if target lesion is treated with XIENCE.
- o If a bailout with an Absorb BVS device cannot be delivered to the site of the lesion, the device should be carefully withdrawn and a XIENCE used.
- o If an appropriate size Absorb BVS is not available XIENCE can be used.

**IMPORTANT:** It is required that the bailout device be placed so that there is no visible gap between the Absorb BVS and the bailout device. In such a case, at least 1 mm (minimum) to 2 mm (maximum) overlap is required.

**IMPORTANT:** In the rare event of acute occlusion following Absorb BVS placement and an additional drug-eluting stent is required for treatment, the bailout device should be XIENCE and deployed within the Absorb BVS such that the Absorb BVS is completely covered by the bailout device if this is believed to be in the best interest of the patient.

Although a bailout procedure is not considered a major adverse cardiac event (MACE) unless the subject sustains death, emergent CABG, PCI or MI, such procedures should be avoided unless required for safe subject management.

### **7.3.6 Final (Post-procedure) Angiography**

Angiographic imaging will also be performed after the Absorb BVS or XIENCE stent deployment. Physicians should follow accepted hospital imaging practice to ensure good apposition of the Absorb BVS or XIENCE to the vessel wall. For angiographic imaging, post-implantation images should be captured the same orthogonal views that were used for the pre-procedure images (after the guidewire has been withdrawn). Intracoronary nitroglycerine should be re-administered before final angiography. If nitroglycerine is not available, intravenous nitroprusside or intravenous calcium channel blocker may be used per physician discretion.

### **7.3.7 Final (Post-procedure) IVUS and OCT**

IVUS and OCT may be performed post-procedure per site standard of care. If stent or scaffold under-expansion or substantial malapposition is seen and post-dilatation required, a non-compliant balloon should be used. Do not dilate the Absorb BVS beyond the dilatation limit which is 0.5 mm above the nominal diameter. Repeat angiography in orthogonal views must be performed after any additional inflations.

